### B.3 Population Trends in Weight

Long-term trends in weight have been tracked in only a few countries. Somewhat surprisingly, what has emerged, as noted above, is a long period of stability until the last two decades of the 20th century when an abrupt upturn took place. In the US, this inflection point is sharply defined at 1985 (cf, Figure 1) [27]. In Norway, for example, the upturn occurred around 1990 [50]. Many developing countries are also experiencing even more rapid increases in relative weight, which in turn have led to an abrupt up-turn in the prevalence of CV risk factors and diabetes. Trend data analyses of longitudinal cohorts in Nigeria, Jamaica, and the US demonstrate that while they all gained weight during follow-up, the rate of change varied markedly with the steepest slope in Jamaica (0.4 kg/y in Nigeria vs. 1.4 kg/y in Jamaica) [51]. The 5 countries selected for our study span the full range of the obesity spectrum (Figure 2). The rapidity of the obesity trends has been particularly striking in developing countries. We would therefore expect that the risk relationships would be most clearly delineated in that setting.

[figure not shown]

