## D. EXPERIMENTAL DESIGN AND METHODS

### D.1 Project Overview

#### D.1.1 Participant Recruitment and Baseline Exam

Population-based samples, ages 25-45, will be drawn from communities in 5 countries: Nigeria, Seychelles, South Africa, Jamaica and the US; 500 per site, 2500 total. Based on our overall experience with

longitudinal studies, we experienced 2% annual attrition in Nigeria and 10% in the US site, we anticipate no more than 20% attrition by the 24-month examination, resulting in a final 'N' of at least 400 per site (Table 5).

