#### D.3.2 Sampling Procedures

In each of the 5 sites, 75 individuals aged 25-45 years will be recruited for the DLW protocol and 425 will be recruited for the accelerometer protocol, with equal numbers of men and women. We will exclude individuals with obvious chronic or infectious diseases (including active malaria), pregnant or lactating women, and HIV positive individuals (see D.3.3 for HIV testing procedures). Any individual that has a condition preventing normal AEE will also be excluded from our study. Population-based surveys have been carried out in each of the sites; the sampling procedures used previously will be employed in the present study. These study sites were chosen because mean BMIs and prevalence of obesity span the healthy physiological range.

Jamaica – Spanish Town is an urban area 25 km from the center of Kingston. Once the capital of colonial Jamaica, Spanish Town is an established community with a population of 92,000 in 1991; about 45,000 individuals are between the ages of 25 and 74. A community-based study of hypertension and diabetes (n=3500) has been completed [123]. Districts were randomly sampled; beginning from a fixed point in each district (e.g., the north-west corner), door-to-door screening took place. Examinations will be carried out in the local health clinic and specimens taken immediately to the Univ. of the West Indies for processing.

US – Maywood is an African-American working class community adjacent to the western border of Chicago, Illinois. Approximately 3,500 participants have been examined in our clinic since 1991 for both observational and interventional studies [123]. Participation rates for observational components of these studies have been 60% or greater. Project staff are residents of the community and conduct all recruitment and home visits. We have now contacted individuals on approximately two thirds of the blocks in Maywood and are well known to the community. The Department clinic is on campus, within walking distance of most neighborhoods and is well known to local residents. We will also recruit from the adjoining west side of Chicago.

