Nigeria – Developed in 1965 as a teaching site for the University College Hospital (UCH), University of Ibadan, Igbo-Ora is a rural community with a population of 50,000 in the Yoruba-speaking region of southwest Nigeria. All permanent houses have been mapped and assigned numbers by public health workers. Most residents are subsistence farmers or petty traders. Loyola has been engaged in collaborative research with the UCH Dept of Social & preventive Medicine since 1992 and maintains a permanent facility in Igbo-Ora. Ten-thousand adults are being followed in a prospective cohort study on hypertension, and 3,000 family members have been enrolled in genetic studies [123, 124, 126, 127]. Prior studies on EE and obesity have been carried out in this community.

Seychelles – The Republic of Seychelles is an archipelago with 81,000 inhabitants located approximately 1,500 km east of Kenya in the Indian Ocean, and approximately 2,000 km north of the island of Mauritius. Population-based surveys in 1989 and 2004 have shown increasing prevalence of several cardiovascular risk factors in the adult population [146, 147]. The sampling method will be a sex- and age-stratified random sample generated from the national census.

South Africa – Khayelitsha, the 3rd largest township in South Africa, is adjacent to the city of Cape Town. The population is about 500,000 people with 80 percent of the residents living in shacks and 40 percent unemployed. There are no hospitals in Khayelitsha, but there are three community health clinics. Investigators in Cape Town have recently been funded to conduct a population-based 5-year prospective study on AEE and diabetes in 1000 members of this urban community. A sex- and age-stratified random sample will be generated from the national census.

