#### D.7.1.3 Comparison of Mean AEE Levels Among Sites

The 2 sample t-test will be used to compare means of the primary continuous variables, e.g., BMI, PA, weight, and height. Relevant co-variates will be identified from the within-site analyses and added using multivariable models [186, 190]. We recognize that some modifying factors within sites may not have the same significance across sites, and we will be very careful how variables are chosen for these analyses. Finally, we will test whether the regression slopes of the PA-BMI relationship varies significantly among any pair of sites (i.e., test for interaction).

The association between mean levels of AEE and mean levels of obesity/relative weight will be assessed using regression analysis, following a meta-regression type of approach. That is, mean AEE values will be regressed on mean obesity/relative weight values, weighting by the inverse of the squared standard error of the mean AEE values [191]. This is a widely-used approach in meta-analysis [192]. It is recognized that EI is an important potential confounder of the associations at the individual level. We will estimate the median (and other quantiles of the distribution) usual intake of nutrients (e.g. fat, percent fat) using methods developed by the ISU research group [179, 193] and include them in the meta-regression models.

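### The Hypothesis 3 meta-regression uses group means that are not age-standardised, and D.3.2 sets no common age allocation across sites, so age composition within 25-45 can distort the ecological AEE-obesity association.

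*Combined protocol and SAP*

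**What the plan says.** **Sampling.** D.1.1 promises population-based samples: "Population-based samples, ages 25-45, will be drawn from communities in 5 countries". D.3.2 asks for equal numbers of men and women and adds that "the sampling procedures used previously will be employed in the present study". Age strata are stated for two sites: for Seychelles, "The sampling method will be a sex- and age-stratified random sample generated from the national census", and for South Africa, "A sex- and age-stratified random sample will be generated from the national census". For Jamaica the text describes a completed survey: "Districts were randomly sampled; beginning from a fixed point in each district", with door-to-door screening. The Nigeria entry mentions mapped and numbered houses, and the US entry describes community recruitment. None of these three mentions age strata. No site, including the two stratified ones, has a stated number or proportion per age band.

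**Analysis.** For Hypothesis 3, D.7.1.3 says that "mean AEE values will be regressed on mean obesity/relative weight values", weighted by the inverse squared standard error of mean AEE. Quantiles of usual dietary intake are to enter these models; no other adjuster is named and age standardisation is not mentioned. An earlier sentence in D.7.1.3 allows covariates found in the within-site analyses to be added when site means are compared, without naming any. D.7.1.1.1 names age as a confounder in the person-level models. D.7.2 adds a secondary test of Hypothesis 3 that compares mean AEE between the most and least obese groups.

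**The concern.** Age is treated as a confounder where the unit is the participant, but not in the analysis with 5 site means (or 10 sex-by-site means). If weight rises with age, a site whose participants are older within the 25-45 window will tend to look heavier for that reason. If activity also changes with age, both axes of the regression move. Equal sex numbers do not prevent this, and stratifying by age does not equalise ages across sites unless the allocation is common.

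At stake is the interpretation of the ecological result. With so few points, a shift in one or two means can change the order of neighbouring sites and hence the slope.

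**Working it through.** **1. The plan's own power figures for Hypothesis 3.** D.7.2 gives over 55%, 80% and over 95% for r = 0.85 with 5, an effective 7, and 10 units. With power = Φ(atanh(0.85)·√(n−3) − z), atanh(0.85) = 1.256 and one-sided 5% z = 1.645:

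- n = 5: Φ(1.777 − 1.645) = 55.2%
- n = 7: Φ(2.512 − 1.645) = 80.7%
- n = 10: Φ(3.324 − 1.645) = 95.3%

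These reproduce the plan. A two-sided 5% test gives 42.7%, 71.0% and 91.4%, so the stated figures are one-sided.

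**2. How far mean age can differ inside 25-45.** A flat age distribution has mean 35.0. If the density falls linearly from 1 at age 25 to r at age 45, the mean is 25 + 20·[1/2 − (1−r)/3] / [1 − (1−r)/2].

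- r = 0.5: 33.9, a gap of 1.1 years
- r = 0: 31.7, a gap of 3.3 years

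Chance alone is small. With SD 20/√12 = 5.77, the 95% range for a difference between two sites is ±1.96·5.77·√(2/500) = ±0.7 years, or ±1.0 with 250 per sex and site. A 2-year gap is used below as an illustration; it lies between the two density cases.

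**3. What a 2-year gap does to mean BMI.** Shift = years × kg/y ÷ height². Weight gains come from B.3 ("0.4 kg/y in Nigeria vs. 1.4 kg/y in Jamaica") and from C.2.2.2 (0.73 and 0.76, taken as 0.75). Heights of 1.60 to 1.75 m are an assumption.

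| Gain (kg/y) | At 1.75 m | At 1.60 m |
|---|---|---|
| 0.4 | 0.8/3.0625 = 0.26 | 0.8/2.56 = 0.31 |
| 0.75 | 1.5/3.0625 = 0.49 | 1.5/2.56 = 0.59 |
| 1.4 | 2.8/3.0625 = 0.91 | 2.8/2.56 = 1.09 |

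**4. Against the between-site contrast.** The population mean BMI rows of Table 1 span 22.6 to 26.7 in men (4.1 units) and 22.9 to 29.8 in women (6.9 units). Some neighbouring sites are close: Nigeria and South Africa differ by 0.3 in men; South Africa, Seychelles and Jamaica differ by 0.5 and 0.4 in women. A shift of 0.3 to 1.1 is small against the full range but similar to, or larger than, these gaps.

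**5. Two ways to handle age.** Direct standardisation leaves the number of units as it is, so the power in step 1 stands for the same r. Entering mean age as a group-level covariate costs one unit, so √(n−3) becomes √(n−4):

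- n = 5: Φ(1.256 − 1.645) = 34.9%
- n = 7: Φ(2.176 − 1.645) = 70.2%
- n = 10: Φ(3.077 − 1.645) = 92.4%

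**The case against.** **The plan already handles confounding.** D.7.1.3 allows covariates when site means are compared, D.7.1.1.1 names age, and D.7.2 recognises ecological confounding and answers it by testing individual-level relationships first. This stands in part. The covariate sentence could bring age into the pairwise comparisons, and so into the test of the most against the least obese groups. But it names no covariate, leaves the choice to the data and does not extend to the meta-regression. Testing person-level relationships first does not remove age composition from group means.

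**Three sites are not shown to lack age control.** This stands. A reader might infer that Jamaica, the US and Nigeria are unstratified. The documents are silent and defer to earlier procedures, and the Jamaican description is of a past survey.

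**The pilot is no forecast.** This also stands. Table 1 shows site mean ages from 27.2 to 38.9, and a reader might take the 11.7-year span as the likely drift. Nigeria's age SD of 13.2 exceeds the largest value possible for 38 people confined to 25-45, 10·√(38/37) ≈ 10.1, so that pilot went outside the window. The outlier, South Africa, is a site that will be stratified. The three sites without stated strata had means of 37.9, 38.3 and 38.9, a spread of 1.0 year.

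**Bias is not demonstrated.** Agreed. Across the five pilot sites, holding mean age fixed moves the correlation of AEE/kg with population BMI only from 0.04 to 0.18 in men and from 0.52 to 0.56 in women. Five points each make this weak evidence either way.

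**Conclusion.** The gap is real but modest: followed as written, the Hypothesis 3 meta-regression uses means that are not standardised for age, drawn from samples with no common age allocation. Age composition can distort the association; the documents do not show that it would create, hide or reverse it.

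An illustrative 2-year gap in mean age is worth about 0.3 to 1.1 BMI units, against spreads of 4.1 and 6.9. This rests on the assumed gap and heights, and on using weight gain over time in place of the cross-sectional age slope. Those gains may mix ageing with secular trend, and B.3 and C.2.2.2 give none for Seychelles or South Africa. Larger shifts, such as those from a 5-year gap, need a difference in mean age that nothing in the documents supports for a 25-45 sample. The size of any effect on AEE is not estimated.

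A reader might also conclude that recruitment must change. It need not: equal age quotas would pull the samples away from each community's own age structure, and age is recorded for every participant (D.3.1).

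**What to change.** In D.7.1.3, pre-specify that each sex-by-site mean of AEE, and of BMI or percent body fat, is directly standardised to one common 25-45 age distribution in 5-year bands, with that distribution stated in advance. Do this before both the meta-regression and the comparison of the most and least obese groups in D.7.2. Take the inverse-variance weights from the standard errors of the standardised means. Report crude means alongside, so that the population-mean reading of Hypothesis 3 is kept.

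The cost is a few lines of analysis on data already collected, and possibly slightly larger standard errors where a site's ages differ from the standard. Accelerometer cells are ample: 250 per sex and site over four bands averages about 62. For the DLW subset, 75 ÷ 2 ÷ 4 is about 9 per band, so wider bands or a regression-based standardisation may be needed there. The number of regression units is unchanged. It would also help to state in D.3.2 how age is handled in Jamaica, the US and Nigeria, but the fix does not depend on it.

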### D.3.3 HIV Testing in South Africa

The prevalence of HIV in the rural regions of Nigeria in which this study will be conducted is less than 2% [148], and less than 1% in the Seychelles [149]; however, the prevalence is as high as 12% in the Western Cape, South Africa [150]. The hyper-metabolic state produced by HIV infection can significantly impact body weight well before other signs of infection appear. In order to eliminate the impact of HIV infection, we will work with the community health clinics in South Africa in which study enrollment will take place. All participants will be tested for HIV and undergo pre- and post-test counseling both before study enrollment at baseline and again at follow-up (cf. E.2.2 Protection Against Risk). The officials at LifeLine Clinic in Khayelitsha, Cape Town, have agreed to counsel, test, and treat all participants in the screening process of this study. All the above options are free of charge in South Africa as a result of both national and international efforts. HIV-positive individuals will be excluded from our study.

## D.4 Measurement Procedures

### D.4.1 Activity Energy Expenditure

Total daily EE is comprised of three components: resting EE, AEE, and thermic effect of food. In this study, we are most interested in AEE and its relationship to weight change and insulin sensitivity. AEE will be measured by two methods: accelerometers and DLW. All participants in each site will wear an activity monitor for 6-9 days, while a subset will undergo the DLW procedure as well. Our previous experience with measurement of EE indicates that both resting EE and AEE are very stable traits, with within-person correlations of 0.9 and 0.8 at intervals of 1-2 years, respectively [135]. For those participants in the DLW

[figure not shown]
subset, resting EE will be measured by indirect calorimetry, and thermic effect of food will be estimated as 10% of total daily EE. All methods are described below.

#### D.4.1.1 Physical Activity by Accelerometer

PA will be measured using the Actical activity monitor (Respironics/Mini-Mitter, Bend, OR) with all participants. Previous studies have shown that accelerometer-based activity monitors can discriminate differing intensities of activity [151-156], making it possible to adequately characterize each of the study communities with regard to overall intensity of PA. We will record the data as activity counts/min and kcal/d. The activity monitor records the intensity, duration and frequency of physical motion through the use of an accelerometer which produces a variable electrical current based on the combination of the amplitude and frequency of motion. Accelerometers are omnidirectional motion sensors that count the vertical and horizontal acceleration of the user. This information is stored within the instrument as activity counts per epoch, or specified subunit of time, e.g., per minute. As the intensity of the activity increases, so does the number of activity counts per epoch. The Actical monitor is lightweight, waterproof and made to be worn on the wrist, waist or ankle. Consistent placement of the activity monitor ensures comparability of data. For this study, the monitor will be worn at the waist. There are concerns about the ability of the accelerometer to discriminate between some activities with differing energy expenditures, eg, stair climbing versus level walking. As described below, our consultants are developing methods to improve accuracy of these instruments.

There is controversy over the number of days of recording needed to adequately capture habitual activity levels; the suggested range is from 4 to 9 days [152]. We used the Spearman-Brown prophecy formula with calculated, site-specific intraclass correlation coefficients [157] to estimate the level of reliability achieved for a given number of days of monitoring in each site (Figure 7) [152]. Most studies use 0.8 as an acceptable level of reliability [152, 158-161]. For our data, all sites achieve this level with five days of monitoring (ie, excluding the first and last partial days of monitoring which are dropped from analysis), however the Seychelles are on the borderline. Given the practicality of six days of monitoring (i.e., participants will receive the monitor and return the monitor on the same day of the week), we have chosen to monitor all participants for six days (i.e., a total of 8 after taking the two partial days into consideration). With six days of monitoring, the expected level of reliability will be 0.83-0.92.

The Actical activity monitor will be initialized for each participant on the morning of the initial clinic examination, using the on-site computer. The participant's ID, epoch period (1 minute), start date and time, and mode will be entered into the main program. Use of the activity monitor will be explained to the participant: the participant will be asked to wear the activity monitor at all times over the next 8 days, including during sleep; the only time the monitor should be removed is while bathing, showering, or swimming. The activity monitor will be placed on the participant on a belt at the waist, positioned just behind the left hip bone. The participant will be trained in proper handling of the accelerometer, including removal and placement of the monitor on the belt as well as placement of the belt on the body, in order to ensure accurate measurements. If the participant has problems sleeping with the monitor, they will be encouraged to remove it during sleep hours. An additional belt will be provided in case it gets wet and needs to be swapped out. Staff members will contact participants within 24 hours after the initiation of the monitoring session to ensure that there is no discomfort with the monitors. In addition, the monitor will be checked at the midpoint home or clinic visit to ensure proper placement and recording. On day 8, each participant will return to the clinic, and the staff member will verify end date and time and download the data. Data will be presented as activity counts per minute for the whole day and during hours the participant is awake, as well as kcal/day or METs/wk in AEE as calculated using the accompanying software [153, 155, 156, 162, 163].

Investigators at each site have significant experience with accelerometer-based activity monitors and with the validation of monitors using the DLW method. Staff will be collectively trained on the use and handling of the Actical. In addition, we will validate the Actical activity monitor for estimation of energy expenditure in AEE at each site through the comparison with DLW results. Validation of this instrument will help in future studies for the quantification of AEE at significantly lower cost than available with DLW.

Over the years, we have had extensive experience with several models of accelerometers, activity monitors, and heart rate monitoring devices. Missing data is a well-documented problem with activity monitors in general and can result from instrument failure or non-compliance of the participant, i.e., the monitor is simply removed for part of the measurement period. In our experience, all cases of truncated data collection (which occurred in less than 2% of participants) had at least 4 days of data collected over the 7-9 day measurement period, providing at least some data for analysis. Methods of handling missing data are further discussed in the analytical section.

The consultants on this project, Drs. [name] and [name], are currently working on advanced methods of analysis for data generated from accelerometers. They have demonstrated that converting the output from accelerometry to units of acceleration (in m/s) from counts provides substantial additional information by capturing speed of motion [130]. After adjustment for built-in frequency filtering by the specific accelerometer model, acceleration is linearly associated with activity counts, as well as with EE. [name] and [name] are also developing methods using Hidden Markov Models and other mathematical approaches to improve the accuracy of accelerometer data, particularly with regard to recognition of patterns of activity that allow further differentiation among activities. The DLW data from this project will therefore help improve the accuracy of accelerometry as a tool in survey research, while improving the precision of the data collected in our project.

